## **F. Alternative Treatment**

The alternative is for participants to not participate in the study

## **G. Consideration of Specific Participant Categories**

### **1. Inclusion of Women**

All participants will be women, as PCOS only occurs in females.

### **2. Inclusion of Minorities**

Every effort will be made to include a diverse participant distribution. PCOS affects Caucasians, Hispanics and African Americans equally.

### **3. Inclusion of Children**

All participants will be between ages 12 and 21. Insulin sensitivity needs to be studied in the adolescent age group as available is scarce in this age group and it is critical to understand the pathophysiology of PCOS in its developing stages.

## **IV. Potential Scientific Problems:**

### **Limitation of Method Development:**

The protocol as described includes an OSTT with an oral tracer will be conducted in all participants. The specific points that are to be evaluated are listed below:

- 1) Measurement of Hepatic Substrate flux in youth during fasting.
  - a. Purpose: Assess hepatic substrate flux in youth looking at shifts from pentose phosphate pathway (PEP), TCA cycle and fatty acid synthesis
  - i. Rational: utilizing and oral glycerol model with NMR isotopomer analysis is a newer technique. We have validated the timing with an OSTT in youth. However, this relies on consistent OSTT responses. When we anticipate that the response to the OSTT may change, the timing and thus results would vary, and we are thus better off using a fasting model. This has been done in adults, but not in our youth.
  - ii. Measurement: NMR isotopomer analysis with pathway flux calculations and modeling in the fasting state
  - iii. Revision plan if model not correct: 1) increase the amount of tracer given 2) increase the frequency of blood draws in the later sampling period.

### **Overall Project Limitations:**

We expect to complete 20 participants in 2.5 years. As with any clinical trial, recruitment and retention can be challenging. We have successfully recruited over 120 obese girls with untreated PCOS, and thus our recruitment goals are in line with previous work. We have never needed to recruit in the community or other endocrinology practices, but can if needed. Within our department we have been successful with 3 month, 21 month and 3 year interventional protocols and we have designed the study with techniques found to be successful in similarly obese adolescent populations. Adherence to treatment is also a challenge, and we will use texting and emails as preferred contacts in youth to send supplement reminders. Major changes to diet and exercise could alter results, and we will request participants not to initiate major lifestyle changes during the study. An alternative would be to recommend lifestyle changes for all girls, although from our clinical experience these are poorly followed.

**Aim 1:** We anticipate that after EAA, absolute IHTG will decrease by 3% compared to placebo, secondary to decreased DNL. Based the mean of  $11 \pm 3.5\%$  IHTG in PCOS girls with HS, this is less than the relative 50% decrease we found in most of older adult participants. Further, 9 days of low fructose dietary modification reduced IHTG by 50% via decreased DNL in obese youth with HS, demonstrating that IHTG can be rapidly changed with dietary modification and relates to decreased DNL. However, this patient population does have a very poor diet, and it is possible that those with excessive soda intake will not benefit as anticipated if EAA cannot overcome the excess glucose. An alternative would be to provide the diet for participants for 3 days prior to studies. We will be using a FibroScan ultrasound based method to determine the presence of HS at screening. MRI is the most sensitive and repeatable measure for IHTG. Ideally we would also perform an MRI for IHTG at screening to determine eligibility, however the cost and time of this for the 50% of girls to be excluded is excessive and the processing time for the results is not conducive for a screening test. Whereas our lab has not used deuterated water to measure DNL, this method has been used successfully in other youth populations by our collaborator [name], and we thus are confident that we will be able to perform this analysis.

Aim 2: We expect that insulin sensitivity will improve following EAA and that the glucose concentration at 2 hours of the OSTT will decrease. The reproducibility of glucose measurement from an OSTT in any individual is only 75%, however, this is when the effects of exercise, diet, sleep and menstrual cycle are not controlled. An alternate approach for assessing insulin sensitivity would be a hyperinsulinemic euglycemic clamp, for which we have extensive experience. We have not elected to use this as it is not physiologic and does not allow for isotopomer assessments. We expect to measure hepatic metabolism with metabolomics and isotopomer analysis and to integrate these results with clinical outcomes. We hypothesize that those with worse HS will have increased futile TCA cycling and increase BCAA which will improve with improved insulin sensitivity and decreases in liver fat after EAA. If our hypotheses are incorrect, the data may suggest additional mechanistic pathways unique to PCOS. Interpretation of the resulting data requires extensive knowledge of biochemistry and I have the unique skills, time, institutional support, collaborators, and mentoring to be successful.

## **V. Data Management and Security Plan**

### **Data Entry**

Data will be entered from paper forms. Once forms are completed, verified and corrected for inconsistencies, they will be manually entered at our site using a computerized data management system (Redcap).

### **Edit Checks**

Computerized data validation routines will be used to enhance data quality and verify the accuracy of data within predefined value ranges. These checks include, but are not limited to: (a) initial screening of data, using logic and range checks built into data entry screens; (b) cross-form functional and consistency checks; and (c) edits assessing the serial integrity of data.

### **Disaster Recovery**

Routine data backup will occur on data in conjunction with the Children's Hospital secure server and Redcaps.

### **Security and Confidentiality**

All hard copy forms will be de-identified with a study number and filed in a locked cabinet, to which only the investigators will have access. Standard protection against computer hackers is implemented. Recovery from natural disasters (water, fire, or electrical) can occur through the ability to reconstruct both the database management system and the data from nightly backups.

## **VI. Data and Safety Monitoring Plan**

The principal investigator and study coordinator will monitor the protocol and the safety of the research participants. The PI will review all laboratory data and report any abnormal values to the patient and guardian and instruct the participant to follow-up with their PCP. If an abnormal result from a research procedure exists, the PI will notify the family and their PCP and refer the participant to the appropriate clinic for further evaluation. The PI may also share research results in a reasonable and prudent manner with appropriate medical professionals if the participant was seriously injured as a result of a procedure or if follow-up of the result of the procedure is in the best interest of the participant's health as determined by a medical professional. If immediate medical follow-up of participant required, the PI will share the research results via EPIC when clinically relevant. The PI will report adverse events, and any decision to suspend or halt the protocol to CTRC and COMIRB immediately. The PI will also prepare a written report for the yearly continuing review required by COMIRB and the CTRC. There are no other entities that require notification about this protocol.

No protected health information will be collected until the appropriate HIPAA forms are completed. The protected health information that will be collected will include: Name and phone number, demographic information (DOB, sex, ethnicity, address, etc.), diagnosis (es), history and physical, laboratory or tissue studies, radiology studies, procedure results, survey/questionnaire results, research visit records, and portions of previous Medical Records that are relevant to this study. This information will be accessible only by the study investigators, Federal agencies overseeing human participant research, the Colorado

Multiple Institutional Review Board, regulatory officials from the institution where the research is being conducted to monitor safety and compliance with policies.

#### **A. Adverse Events (AE)**

The OSTT is a standard procedure used in a large number of research studies and settings. Adverse events are uncommon when the procedure is done by experienced personnel in an appropriate setting.

##### **1. Adverse Event Definition**

For the purposes of this study, an Adverse Event (AE) is defined as any significantly abnormal physical finding identified on examination and any significantly abnormal laboratory result obtained on the patient between visits or at the time of the visit. Questions answered YES and any new abnormal physical findings are pursued by the study staff in order to determine the seriousness of the event and the need for further evaluation, follow-up, or referral. If follow-up or referral of abnormal research results or procedure is required, the PI will place a referral in EPIC, update the PCP on patient condition and reason for referral and contact family to discuss follow-up treatment options.

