## 3. Oral Sugar Tolerance Test (OSTT):

*Description:* An OSTT will be performed with multiple blood draws. The purpose of the OSTT is to provide a controlled oral stimulus to effect changes in lipolysis and hepatic glucose release.

*Risk:* The participants rarely experience nausea within 15 min of consuming the drink, however, the amount of carbohydrate is very similar to a large soda, which is regularly consumed by this patient population.

*Justification/Minimization:* A standard oral challenge is needed to study lipogenesis, lipolysis and gluconeogenesis in the fed state. We have chosen to start with a standard glucose and fructose load, to simplify the mathematical modeling. Dynamic carbohydrate metabolism in youth is made more relevant by the recently reported TODAY study, showing a decline in beta cell function in youth with newly diagnosed type 2 diabetes that was much more rapid than what has been reported in adults, and not prevented by metformin in the majority of the youth. Our team of investigators, CTSC research nursing staff and physicians are well experienced with the OSTT blood draw procedure. A floor nurse located on the will be available during our inpatient visits and patients will be distracted by TV or other similar means during the OSTT, to minimize queasiness.

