##### **a) Adverse Event Reporting**

AEs are reported on a standard form that is completed by the study staff at each regular follow-up visit and phone interview. Adverse events reported or ascertained between clinic visits are captured and reported at the time of the next scheduled visit.

Pre-existing conditions (that is, conditions present prior to study enrollment) are not considered or recorded as AEs or SAEs unless the condition worsens in intensity or frequency after enrollment. Likewise, continuing adverse events are not reported as AEs at subsequent visits unless they increase in severity or frequency between the visits, they result in criteria for an SAE, and/or they resolve between visits.

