#### **B. Serious Adverse Events (SAE)**

##### **1. Serious Adverse Event Definition**

Events are divided into those that are not serious (AE) and those that are serious (SAE). The distinction between an SAE and an AE is a regulatory definition established by the FDA, not a clinical definition. The definition of SAE is not always related to clinical severity of the event. For the purposes of this study an AE is considered a Serious (SAE) when it satisfies any one of the following criteria:

- The event results in an inpatient hospitalization (any overnight stay associated with an admission).
- The event results in the prolongation of a hospital stay.
- The event results in permanent or severe disability.
- The event results in death.
- The event is life-threatening.
- Treatment is required to prevent a serious event.

There have been no SAE's in the research groups experience in the Pediatric CTRC. We do not anticipate encountering SAE's; however, we have identified the following as possible SAE's for the purposes of monitoring:

- Infection related to blood draw or IV placement

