## **VIII. Summarize Knowledge to be Gained:**

**Overall Expected Results:** We anticipate that we will determine which specific areas of hepatic metabolism are upregulated in girls with hepatic steatosis and can these be changed with EAA supplementation. This data would then provide the background evidence for future larger therapeutic trials. We will also continue to refine the isotopomer protocol with extension into fasting.

**Significance:** Recent evidence in adults with PCOS indicates that 60-70% have NAFLD. Our data shows that > 45% of obese girls with PCOS have NAFLD, likely an underestimate due to exclusion criteria of T2D and weight >250 lbs in the previous protocols. The majority of NAFLD studies have focused on males, and none have been performed in multi-race cohorts of girls with PCOS, despite this high prevalence. NAFLD has been described as the primary driver of worsening metabolic syndrome and CVD in obesity across populations, and can progress to cirrhosis and liver failure. Thus, understanding the hepatic metabolism associated with NAFLD is critical to designing strategies to improve the long-term health of these girls and reduce their risk of T2D, CVD and liver failure. Further, we will be testing a well-tolerated oral nutritional supplement.

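### The adverse event definition covers only examination and laboratory abnormalities, while the collection text implies that symptoms are elicited; the two must be reconciled so that symptoms are counted

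*Combined protocol and SAP*

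**What the plan says.** Section VI.A.1 (Adverse Event Definition) opens with the controlling sentence, which defines an adverse event for this study as "any significantly abnormal physical finding identified on examination and any significantly abnormal laboratory result", obtained between visits or at a visit. The next sentence concerns follow-up: "Questions answered YES and any new abnormal physical findings are pursued by the study staff in order to determine the seriousness of the event" and whether further evaluation or referral is needed. The questions themselves are not described.

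The reporting subsection that follows says "AEs are reported on a standard form that is completed by the study staff at each regular follow-up visit and phone interview". It adds: "Adverse events reported or ascertained between clinic visits are captured and reported at the time of the next scheduled visit". It also excludes conditions present before enrollment unless they worsen in intensity or frequency after it, so the recording clock starts at enrollment.

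Section VI.B.1 builds seriousness on the same term: "For the purposes of this study an AE is considered a Serious (SAE) when it satisfies any one of the following criteria".

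The Study Calendar in Section III.C lists a history and physical at Visit 1 only and has no row for adverse events. The Visit 3 description, which Visit 5 repeats, has participants asked about changes in medication and medical history and has height, weight and blood pressure recorded. Section VII contains no tabulation or comparison of adverse events.

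**The concern.** The supplement is a drink taken at home twice a day for four weeks. If it causes problems, many would be known only because the girl says so: nausea, bloating or headache, for example. These are illustrations. The documents itemise no EAA side effect and name nausea only for other drinks: for the sugar drink, "The participants rarely experience nausea within 15 min of consuming the drink", and similarly for deuterated water. They do show that this kind of event is foreseen in the study.

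On the first sentence of VI.A.1, such a complaint is not an adverse event unless an examination or a laboratory test is also abnormal. On the sentences that follow, staff appear to ask about complaints and act on them. Two members of staff could read the same section and log the same event differently. What is at stake is the completeness and consistency of safety reporting in a placebo-controlled trial that enrols girls from age 12, and with it the ability to set EAA and placebo periods side by side.

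**Working it through.** No arithmetic applies and the plan gives no figure to reproduce. The check is to set the passages side by side and follow one event through them: nausea on several mornings in the second week of a treatment period, with no abnormal finding.

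1. **Does it meet the definition (VI.A.1, first sentence)?** There are two limbs, an abnormal physical finding on examination and an abnormal laboratory result. Reported nausea is neither. No other part of the safety plan or of the procedure-risk section (III.D) widens the definition.

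2. **Would an examination turn it into a finding?** There is little scheduled opportunity. The calendar's only history and physical is at Visit 1, before dosing. The on-treatment visits list history questions, height, weight, blood pressure, imaging and blood sampling.

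3. **Would staff hear of it?** Probably. A positive answer to a question is to be pursued, and VI.A.1 lists such answers separately from new physical findings. AE forms are completed at phone interviews, which cannot yield an examination or laboratory result. Events reported between visits are to be captured. All three routes make most sense if participants' own reports are meant to count.

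4. **Would it be recorded as an AE?** Here the text divides. By the definition, no. By the collection procedure, apparently yes. The sentence on positive answers tells staff to judge seriousness and follow-up; it does not say that the answer is an AE.

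5. **Could it be placed in the right period?** Not reliably. Between-visit events are logged at the next scheduled visit. The schedule is 4 weeks of treatment, Visits 2 and 3, about 4 weeks of washout, 4 weeks of the other treatment, then Visits 4 and 5. An event early in washout may therefore be logged about 4 + 4 = 8 weeks later, at Visit 4, when the second treatment has been taken. The documents do not say that the form records an onset date.

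6. **Does the SAE rule matter?** Only slightly. The sentence introducing the criteria starts from an AE, so on a literal reading the gap is inherited. The same section also divides events in general into serious and not serious, and most of its criteria refer simply to the event.

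Steps 1, 3 and 4 establish the point: the definition is narrower than the procedure that feeds it.

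**The case against.** The strongest reply is that the safety plan, read as a whole, already reaches symptoms. Positive answers are pursued, phone interviews are a recording occasion, reported events are captured, medical history is asked about at the overnight visits, and the reporting rules speak of intensity, frequency and severity, terms that suit symptoms better than laboratory values. This stands as evidence that symptoms are elicited. It does not make them adverse events, because the one sentence that says what counts leaves them out.

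Three stronger readings are tempting and are not supported.

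- A reader might infer that no symptom would ever be counted, and that the trial would report almost no adverse events whatever the true tolerability. The AE form and its questions are not in the documents, and the collection text points the other way. A calculation from an assumed symptom rate would rest on that same unproven premise and on a rate that the documents do not give.
- A reader might infer that serious events would be missed. An event leading to admission, disability, death or threat to life would usually bring an abnormal examination or laboratory result and so qualify even on the narrow wording. Participants are also told to contact the clinic about serious events.
- A reader might infer that the trial could not support a planned conclusion, because Section VIII says "Further, we will be testing a well-tolerated oral nutritional supplement". That sentence describes the product going in. Tolerability is not a stated aim or outcome.

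The absence of a planned comparison does not remove the point. Adverse events will still be recorded and reported, and the count should mean the same thing whoever makes it.

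**Conclusion.** The point holds as a conflict between definition and procedure. Applied literally, non-serious symptoms in the EAA or placebo periods are pursued but not counted as adverse events, so AE counts could understate tolerability problems. This assumes only that staff follow the first sentence of VI.A.1 as written; if they count reported symptoms anyway, the fault is one of inconsistent wording. No number can be put on the undercount, because the documents supply neither a symptom rate on EAA nor the content of the AE form. The SAE consequence is minor. Hepatic fat, the primary outcome, is untouched. The change is worth making because it is specific and cheap, and improves safety capture in a trial that includes minors.

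**What to change.** - **VI.A.1, first sentence.** Define an AE as any untoward symptom, sign, diagnosis or clinically significant laboratory change after enrollment, whether or not thought related to the supplement or a procedure. The start should be enrollment, as the reporting subsection already implies, and not the first dose. Otherwise a complication of the Visit 1 blood draw would be lost, although infection from a blood draw is the kind of event VI.B.1 singles out for monitoring.
- **AE form.** Record the onset date. Staff are blinded, so the form needs only the date; events can be assigned to EAA, washout or placebo from the dispensing record at analysis.
- **Section VII.** Add one table of AEs by period (EAA, washout, placebo), with a line for events between enrollment and first dose.
- **VI.B.1.** As a minor consistency edit, state that the SAE criteria apply to any event meeting the reworded definition.

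The cost is one reworded sentence, one field on an existing form, one table and one clarifying clause. The downside is that more minor events will be logged.

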##### **a) Adverse Event Reporting**

AEs are reported on a standard form that is completed by the study staff at each regular follow-up visit and phone interview. Adverse events reported or ascertained between clinic visits are captured and reported at the time of the next scheduled visit.

Pre-existing conditions (that is, conditions present prior to study enrollment) are not considered or recorded as AEs or SAEs unless the condition worsens in intensity or frequency after enrollment. Likewise, continuing adverse events are not reported as AEs at subsequent visits unless they increase in severity or frequency between the visits, they result in criteria for an SAE, and/or they resolve between visits.

#### **B. Serious Adverse Events (SAE)**

##### **1. Serious Adverse Event Definition**

Events are divided into those that are not serious (AE) and those that are serious (SAE). The distinction between an SAE and an AE is a regulatory definition established by the FDA, not a clinical definition. The definition of SAE is not always related to clinical severity of the event. For the purposes of this study an AE is considered a Serious (SAE) when it satisfies any one of the following criteria:

- The event results in an inpatient hospitalization (any overnight stay associated with an admission).
- The event results in the prolongation of a hospital stay.
- The event results in permanent or severe disability.
- The event results in death.
- The event is life-threatening.
- Treatment is required to prevent a serious event.

There have been no SAE's in the research groups experience in the Pediatric CTRC. We do not anticipate encountering SAE's; however, we have identified the following as possible SAE's for the purposes of monitoring:

- Infection related to blood draw or IV placement

